Exclusion criteria (key)	
Patients eligible for this study must not meet any of the following criteria:
 

Prior exposure to TIM-3 directed therapy at any time. Prior therapy with immune checkpoint inhibitors (e.g. anti-CTLA4, anti-PD-1, anti-PD-L1, or anti-PD-L2), cancer vaccines are allowed only if the last dose of the drug was administered more than 4 months prior to enrollment

Previous treatment for intermediate, high or very high risk myelodysplastic syndromes (based on IPSS-R) with chemotherapy or other antineoplastic agents including lenalidomide and hypomethylating agent (HMAs) such as decitabine or azacitidine or INQOVI (oral decitabine) (patients who had up to 1 cycle of HMAs can be included). However, previous treatment with hydroxyurea is permitted.

Diagnosis of acute myeloid leukemia (AML) including acute promyelocytic leukemia and extra-medullary acute myeloid leukemia based on WHO 2016 classification (Arber et al 2016).

Diagnosis of Chronic myelomonocytic leukemia (CMML), or primary or secondary myelofibrosis based on 2016 WHO classification (Arber et al 2016).

History of organ transplant or allogenic hematopoietic stem cell transplant

Participants with prior malignancy, except:

Participants with history of lower risk MDS treated by supportive care (e.g. growth factors, TGF-beta agents) or untreated are eligible

Participants with history of lower risk MDS who were treated adequately with lenalidomide and then failed are eligible

Participants with history of adequately treated malignancy for which no anticancer systemic therapy (namely chemotherapy, radiotherapy or surgery) is ongoing or required during the course of the study. Participants who are receiving adjuvant therapy such as hormone therapy are eligible.

Participants with Myelodysplastic syndrome (MDS) based on 2016 WHO classification (Arber et al 2016) with revised International Prognostic Scoring System (IPSS-R) <math>\leq 3</math>

Investigational and reference therapy	Primary Product: MBG453 (sabatolimab) Secondary Product: Hypomethylating agents approved in the United States for MDS (IV Decitabine or Azacitidine /SC Azacitidine /Oral Decitabine)
Safety assessments	Incidence and severity of AEs and SAEs, changes in laboratory values and vital signs

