Efficacy assessments	

1. Complete remission (CR) rate according to International Working Group (IWG) for MDS (2006) * as per investigator assessment by 12 months.

2. PFS rate is defined as time from enrollment to disease progression (including transformation to leukemia per WHO 2016 classification), relapse from CR according to IWG-MDS * or death due to any cause, whichever occurs first, as per investigator assessment ** by 12 months

3. Overall survival rate, time from enrollment to death due to any cause by 24 months.

4. Time from enrollment to <math>\geq 20\%</math> blasts in bone marrow/peripheral blood (per WHO 2016 classification) or death due to any cause

5. Percentage of CR/mCR/PR according to IWG-MDS as per investigator assessment

6. Time from the date of the first documented CR to the date of first documented relapse from CR or death due to any cause, whichever occurs first

7. Time from enrollment to the first documented CR

8. Number and percent of participants who are RBC/platelets transfusion independent after enrollment as per IWG-MDS

Other assessments	

1. [REDACTED]

2. [REDACTED]

3.

A) [REDACTED]

B) [REDACTED]

4. [REDACTED]

5. [REDACTED]

Data analysis	Data from all participating centers will be combined. Data from all centers participating in this study will be aggregated for analyses. Novartis will conduct all analyses and will report data from all centers.

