### 5.2 Exclusion criteria

Patients eligible for this study must not meet **any** of the following criteria:

1. Prior exposure to TIM-3 directed therapy at any time. Prior therapy with immune checkpoint inhibitors (e.g. anti-CTLA4, anti-PD-1, anti-PD-L1, or anti-PD-L2), cancer vaccines are allowed only if the last dose of the drug was administered more than 4 months prior to enrollment.
2. Previous treatment for intermediate, high or very high risk myelodysplastic syndromes (based on IPSS-R) with chemotherapy or other antineoplastic agents including lenalidomide and hypomethylating agent (HMAs) such as decitabine or INQOVI (oral decitabine) or azacitidine (patients who had up to 1 cycle of HMAs can be included). However, previous treatment with hydroxyurea is permitted.
3. History of severe hypersensitivity reactions to any ingredient of study drug(s) (azacitidine, decitabine, INQOVI (oral decitabine) or MBG453 (sabatolimab)) or monoclonal antibodies (mAbs) and/or their excipients.
4. Current use or use within 14 days prior to enrollment of systemic, steroid therapy (>10 mg/day prednisone or equivalent) or any immunosuppressive therapy. Topical, inhaled, nasal, ophthalmic steroids are allowed. Replacement therapy, steroids given in the context of a transfusion are allowed and not considered a form of systemic treatment.
5. Investigational treatment for MDS received within 4 weeks or 5 half-lives of this investigational treatment, whatever is longer prior to enrollment. In case of a checkpoint inhibitor: 4 months minimum prior to enrollment interval is necessary to allow enrollment.
6. Active autoimmune disease requiring systemic therapy (e.g. corticosteroids).
7. Live vaccine administered within 30 days prior to enrollment. (refer to Exclusion criteria 1 regarding cancer vaccines)
8. Treatment with drugs that are metabolized by cytidine deaminase within 7 days prior to starting the study treatment.
9. Diagnosis of acute myeloid leukemia (AML) including acute promyelocytic leukemia and extra-medullary acute myeloid leukemia based on WHO 2016 classification (Arber et al 2016).
10. Diagnosis of Chronic myelomonocytic leukemia (CMML), or primary or secondary myelofibrosis based on 2016 WHO classification (Arber et al 2016).
11. History of organ transplant or allogenic hematopoietic stem cell transplant

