Disease progression	
At least 1 of the following criteria is met:
 
[In absence of another explanation not due to MDS, such as acute infection, bleeding, hemolysis, etc. Note that observation of peripheral blasts is not a sufficient criterion for progression. However in that case, a bone marrow examination should be made to determine whether relapse has occurred.]
 
Bone marrow according to the number of blasts of the participant at baseline:
 
 
1. Less than 5% blasts at baseline: <math>\geq 50\%</math> increase in blasts over baseline to <math>>5\%</math> blasts
 
2. 5%- <math><10\%</math> blasts at baseline: <math>\geq 50\%</math> increase over baseline to <math>>10\%</math> blasts
 
3. 10%- <math><20\%</math> blasts at baseline: <math>\geq 50\%</math> increase over baseline to <math>>20\%</math> blasts. Participants with more than 20% of blasts will be considered to have transformation to acute leukemia per 2016 WHO classification (Arber et al 2016)
 
 
Peripheral blood:
 
 
1. Decrease of <math>\geq 50\%</math> from maximum remission/response*** levels in neutrophils AND neutrophils <math><1.0 \times 10^9/L</math>. Note: neutrophils counts during periods of active infection will not be considered in determining the maximum
 
2. Decrease of <math>\geq 50\%</math> from maximum remission/response*** levels in platelets AND platelets <math><100 \times 10^9/L</math>
 
3. Reduction from maximum remission/response*** levels in Hgb by <math>\geq 2\text{g/dL}</math> AND Hgb <math><10\text{g/dL}</math>
 
 
Becoming transfusion dependent**
 
Occurrence of acute leukemia or extramedullary leukemia per investigator's judgement

----------------------------	---

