### **12.5.1.4 Leukemia-free survival**

Leukemia-free survival (LFS) is the time from the enrollment date to  $\geq 20\%$  blasts in bone marrow/peripheral blood (per WHO 2016 classification) or death due to any cause.

For a patient without event, the time is censored at the latest date the patient was known to be alive and without leukemia (on or before the cut-off date).

LFS will be analyzed using the Kaplan-Meier Product-Limit method. Patients who are not known to be alive without leukemia will be censored at the last adequate assessment. Estimates

of the 25th, median and 75th percentile of the PFS and their 95% confidence intervals will be provided, if applicable.

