2.7.1.4 Leukemia-free survival

Leukemia-free survival (LFS) is the time from the date of enrollment (cycle 1 day 1) to $\geq 20\%$ blasts in bone marrow/peripheral blood (per WHO 2016 classification) or death due to any cause.

For a subject without event, the subject is censored at the latest date the subject was known to be alive and without leukemia (last adequate assessment, bone marrow and/or hematology assessment on or before the cut-off date).

LFS will be analyzed using the Kaplan-Meier Product-Limit method. Estimates of the 25th, median and 75th percentile of the PFS and their 95% confidence intervals will be provided, Kaplan-Meier curves will be produced, if applicable.

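### Leukemia-free survival leaves out extramedullary leukemia with fewer than 20% blasts, which the same documents treat as AML at entry and as disease progression

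*Protocol*

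**What the plan says.** **The LFS event.** The protocol summary (efficacy item 4), protocol Table 2-1 and section 12.5.1.4, and SAP Table 1-1 and section 2.7.1.4 all give the same two components: at least 20% "blasts in bone marrow/peripheral blood (per WHO 2016 classification) or death due to any cause".

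**Leukemia at entry.** Exclusion criterion 9 in protocol section 5.2 reads "Diagnosis of acute myeloid leukemia (AML) including acute promyelocytic leukemia and extra-medullary acute myeloid leukemia based on WHO 2016". Extramedullary disease is thus AML for eligibility.

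**Leukemia as progression.** The last progression criterion in protocol Table 8-2, repeated in SAP Table 2-6, is "Occurrence of acute leukemia or extramedullary leukemia per investigator's judgement". Progression is a PFS event.

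**LFS censoring.** Protocol section 12.5.1.4 says: "For a patient without event, the time is censored at the latest date the patient was known to be alive and without leukemia". The SAP makes this the latest date "known to be alive and without leukemia (last adequate assessment, bone marrow and/or hematology assessment on or before the cut-off date". Neither LFS section censors at progression or at the start of new therapy.

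**Status.** LFS is secondary objective 4, stated as a rate by 12 months. It is summarised by Kaplan-Meier, and no hypothesis test is planned (protocol 12.4.2, SAP 2.7.2).

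**The concern.** A participant whose leukemia appears outside marrow and blood, with blasts below 20% in both, has developed leukemia by the documents' own entry and progression wording. That participant has a PFS event on that day and no LFS event. An endpoint named leukemia-free survival would then count time after a documented leukemia as leukemia-free, or drop the participant from the risk set because of it.

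The reference to WHO 2016 in the LFS definition does not clearly close the gap. It qualifies a blast percentage, and protocol sections 6.1.4.1 and 9.1.1 themselves explain acute leukemia per WHO 2016 as at least 20% blasts in marrow or blood. A programmer following the SAP would derive LFS from blast counts and death dates.

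At stake are the 12-month LFS rate and the LFS quartiles, with an error that can go only one way.

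**Working it through.** **No plan figure to reproduce.** The documents state no LFS rate, LFS event count or extramedullary rate. The only sample-size figure, 81, concerns adverse-event precision: 1.96² × 0.3 × 0.7 / 0.10² = 80.67, rounded up to 81. It reproduces but does not bear on LFS.

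**What happens to one case.** Take extramedullary leukemia with under 20% blasts in marrow and blood.

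1. The participant dies or reaches 20% blasts by the cut-off. This is an LFS event, dated later than the leukemia.
2. Neither happens. The participant is censored. The date depends on what the rule means by being without leukemia:
   - if extramedullary disease counts as leukemia there, censoring falls before onset;
   - if the SAP's parenthesis governs, censoring can fall at a later marrow or hematology assessment with under 20% blasts.

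Whether a later 20% blast count would be seen is also uncertain. Protocol 8.3 (extension phase) and 9.1.5 stop response assessments at progression, while 9.1.1 continues efficacy assessments after treatment discontinuation without exempting progression.

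**Illustration of size.** From the documents: N = 39 (SAP 1.1). Assumed: m = 8, 12 or 16 other LFS events evenly spaced over 12 months; k extramedullary cases at month 6; no other censoring before month 12. Half of the m events precede month 6.

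- Counted at onset: S(12) = (39 − m − k)/39
- Censored just before onset: S(12) = [(39 − m/2)/39] × [(39 − m − k)/(39 − m/2 − k)]
- Kept at risk, no event by month 12: S(12) = (39 − m)/39
- Death at month 10: S(12) = (39 − m − k)/39

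For m = 12, k = 1:

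- counted at onset, 26/39 = 66.7%
- censored before onset, (33/39) × (26/32) = 68.8%
- kept at risk, 27/39 = 69.2%
- death at month 10, 26/39 = 66.7%

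| m | k | Counted at onset | Censored before onset | At risk, no event by month 12 | Death at month 10 |
|---|---|---|---|---|---|
| 8 | 1 | 76.9% | 79.2% (+2.3) | 79.5% (+2.6) | 76.9% (0.0) |
| 12 | 1 | 66.7% | 68.8% (+2.1) | 69.2% (+2.6) | 66.7% (0.0) |
| 16 | 1 | 56.4% | 58.3% (+1.9) | 59.0% (+2.6) | 56.4% (0.0) |
| 8 | 3 | 71.8% | 78.5% (+6.7) | 79.5% (+7.7) | 71.8% (0.0) |
| 16 | 3 | 51.3% | 56.8% (+5.5) | 59.0% (+7.7) | 51.3% (0.0) |

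Censoring between onset and month 12 gives a value between the censored and at-risk columns. In no column does the as-written rule give a lower LFS than counting the leukemia at onset.

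**The case against.** The strongest reply is that the narrower event may be deliberate. It is worded alike in all five places, it rests on an objective threshold, and the protocol elsewhere explains acute leukemia in blast terms. Two endpoints may legitimately have different events. That stands as a possibility, but the documents do not state such a choice, and their entry and progression wording points the other way. If it is intended, the SAP should say so and fix the censoring date.

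A reader might infer something stronger: that LFS counts only blast percentage, and that every extramedullary case is censored just before its leukemia. The documents do not support that. Death from any cause is an LFS event. Survival is followed to the end of the study (protocol section 3), and LFS is not censored at progression or new therapy. A case that dies or reaches 20% blasts by the cut-off is therefore still an event. For the rest, censoring before onset is one reading; the SAP's tie to a marrow or hematology assessment allows a later date. Nor does 1/39 = 2.6 points measure the censored case. It is the effect of keeping the participant at risk without an event; censoring before onset gives 1.9 to 2.3 points in the illustration.

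It also stands that LFS is descriptive, and that changing an event after database lock needs care.

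**Conclusion.** The gap is real. Extramedullary leukemia with under 20% blasts is a PFS event but not an LFS event at onset. The participant's LFS event is then dated late, or the participant is censored under an ambiguous rule. Every reading leaves LFS unchanged or overstates it.

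The size is unknown and may be zero, because no extramedullary rate is given. Under the stated assumptions, each case without a later event by month 12 adds about 1.9 to 2.6 points to the 12-month rate. A case that dies by month 12 adds nothing to that rate, although its later date can still lengthen the Kaplan-Meier quartiles. No alpha, power or sample-size calculation is affected.

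**What to change.** In the protocol summary, Table 2-1 and section 12.5.1.4, and in SAP Table 1-1 and section 2.7.1.4, add documented extramedullary leukemia as an LFS event, dated at first documentation. It should refer to the last progression criterion of protocol Table 8-2 and SAP Table 2-6. Give leukemia the same meaning in the censoring rule.

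The current SAP addendum is recorded as made after database lock. The widened LFS should therefore be reported beside the as-written version, labelled post-lock, with the number of participants reclassified. If that number is zero, one sentence settles the matter.

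**Cost.** Wording in five places and one further derivation. LFS may come out slightly less favourable. The SAP says response categories are captured in the eCRF but does not say that the criterion behind each progression is, so the recorded data may need checking.

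Separately, protocol 6.1.4.1 words acute leukemia by blast percentage alone, while Table 8-2 also names extramedullary leukemia and investigator judgement. The two differ and must be reconciled by the sponsor's clinical team; this review takes no position on which applies.

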## 1 Introduction

### 1.1 Background

It is estimated that 15,000 to 20,000 new cases of Myelodysplastic Syndromes (MDS) are diagnosed annually in the USA ([Klepin 2016](#)). The incidence of MDS is more frequent in male patients and increases with age, with a median age at diagnosis of about 70 years. MDS correspond to a heterogeneous group of hematopoietic diseases that are associated with impaired bone marrow function, ineffective hematopoiesis, elevated bone marrow blasts and persistent peripheral blood cytopenias. Cytogenetics abnormalities are frequently present at time of diagnosis. Patients with MDS have a predisposition to developing acute myeloid leukemia (AML) ([Heaney and Golde 1999](#)). Although progression to AML can frequently lead to death in patients with MDS, many deaths are consequences of cytopenias and marrow failure in the absence of leukemic transformation. To account for disease heterogeneity, assess the risk of progression to AML and estimate survival, MDS prognostication systems have been proposed. Prognosis is usually determined using the revised International Prognostic Scoring System (IPSS-R), which considers the percentage of bone marrow blasts, the number of cytopenias, and bone marrow cytogenetics. Patients with untreated MDS are stratified into five IPSS-R prognostic risk categories: very low, low, intermediate, high and very high, with median survival times of 8.8, 5.3, 3.0, 1.6 and 0.8 years, respectively and with 25% AML transformation rate of NR (not reached), 10.8, 3.2, 1.4, 0.73 years respectively ([Greenberg et al 2012](#)). In a large database of MDS patients (n = 7,012) distribution of patients across the 5 IPSS-R risk categories were as follows: Very low (19%), low (38%), intermediate (20%), high (13%) and very high (10%) ([Greenberg et al 2012](#)). Current treatment guidelines for MDS recommend modification of the disease with hematopoietic stem cell transplantation (HSCT, treatment with a curative intent), hypomethylating agents (HMA: azacitidine or decitabine) or intensive chemotherapy ([Fenaux et al 2014](#)). Choice of therapy is mainly driven by the IPSS-R score, the overall general health status and clinical assessment of comorbidities. For patients eligible for intensive therapy, and for whom a donor is available for HSCT or for whom the marrow blast count requires reduction, intensive chemotherapy may be considered ([Steensma 2018](#)). HSCT remains the only curative option for MDS patients; however, many MDS patients are not candidate for HSCT ([Passweg et al 2011](#); and see [Section 4.3.1](#)). In MDS patients without major co-morbidities who are classified as intermediate, high, very high risk by IPSS-R, and who do not qualify for HSCT or intensive chemotherapy, HMAs remain the first-line reference treatment. HMAs (azacitidine or decitabine) are generally administered for a minimum of 6 cycles (repeat cycle after 4 weeks), and continued for as long as the patient benefits. HMAs (azacitidine or decitabine) have a similar safety profile. In clinical practice, bone marrow suppression is the most common adverse reaction in demethylation therapy, and is also the main reason for the dose-reduction or discontinuations of decitabine or azacitidine. Supportive care, including blood transfusions, is frequently required. HMAs have improved outcomes for patients with intermediate/high risk/very high risk MDS; especially for patients who are not candidates for intensive chemotherapy regimens or HSCT. However, despite these improvements, prognosis for patients treated with HMA remains poor. Complete Remission rate (CR) with azacitidine or decitabine in higher-risk (IPSS; intermediate- & high, IPSS-R; intermediate, high & very high) MDS is rare. CR rate has been shown to be 9% for decitabine and 17 % for azacitidine in pivotal trials ([Kantarjian et al 2006](#), [Fenaux et al 2009](#)). Other trials

reported CR rate in MDS patients ranging from 7% to 25% with azacitidine and from 9% to 35% with decitabine. ([Sauntharajah 2013](#)).

Zeidan et al reported that azacitidine and decitabine used in monotherapy lead to similar clinical effectiveness and safety profiles retrospective study identified patients diagnosed with MDS between 2004 and 2011 in the US (SEER-Medicare linked database) who received  $\geq 10$  doses of either HMA for comparing clinical effectiveness in daily practice of azacitidine versus decitabine. Azacitidine was used for treating approximately 80% of the patients (n = 2,025). Survival from HMA initiation was estimated with Kaplan-Meier methods and adjustment was made for relevant covariates. No significant survival difference was found between azacitidine and decitabine in MDS patients, including in MDS patients with excess of blasts. However, it cannot be ruled out treatment outcome of a novel compound given in a combination regimen may vary with nature of the partner drug

Both DEC and AZA require IV infusion for 1 hour or subcutaneous (SC) injections daily for 5-7 days of every 28-day treatment cycle. They both have limited oral bioavailability due to rapid degradation by cytidine deaminase (CDA) in the gut and liver. An orally bioavailable HMA option could reduce clinic visit frequency and reduce infusions/injections related adverse events and burden. ASTX727 is an oral tablet comprised of a fixed-dose combination (FDC) of CDA inhibitor cedazuridine (C) at 100 mg with DEC at 35 mg. In a phase 2 study, INQOVI (oral decitabine) (ASTX727) demonstrated pharmacokinetic (PK) AUC exposure similar to IV-DEC at 20mg/m^2 with comparable clinical activity and safety ([Garcia-Manero, MDS Int'l symposium, 2019](#)). At ASH 2019 phase 3 study (ASCERTAIN) demonstrated that INQOVI (oral decitabine), the oral FDC of cedazuridine/decitabine (100 mg/35 mg) resulted in an equivalent DEC exposure to IV-DEC at 20 mg/m^2 over 5 days. Safety findings are consistent with those anticipated with IV-DEC with no clinically significant GI toxicity. Preliminary clinical activity is also consistent with published data from IV-DEC. INQOVI (oral decitabine) is an oral HMA alternative to IV-DEC ([Garcia-Manero et al 2019](#)). The FDA has granted a priority review designation to a new drug application (NDA) for cedazuridine plus decitabine (ASTX727; INQOVI (oral decitabine) for the treatment of adult patients with previously untreated intermediate- and high-risk myelodysplastic syndromes (MDS) or chronic myelomonocytic leukemia (CMML) (accessed at: Astex Pharmaceuticals announces U.S. Food and Drug Administration (FDA). In July 2020, INQOVI has received FDA approval for adult patients with MDS, including previously treated and untreated, de novo and secondary MDS with the following French-American-British subtypes (refractory anemia, refractory anemia with ringed sideroblasts, refractory anemia with excess blasts, and chronic myelomonocytic leukemia [CMML]) and intermediate-1, intermediate-2, and high-risk International Prognostic Scoring System groups. CC486 (ONUREG) only has data in AML patients and is out of scope for this trial, which is why this molecule was excluded from this study.

**Table 1-1      ASTX Oral Decitabine Safety: Most Common All Grades AEs in the First 2 Randomized Cycles (All Causality) – Garcia Manero et al ASH 2019**

None of the differences was statistically significant (All P values  $\geq 0.10$ )

GI AEs Grade  $\geq 3$  incidence  $<1\%$  for each of ASTX727 and IV decitabine in Cycles 1 or 2

Patients, n (%)	IV Decitabine Cycle 1 or 2	ASTX727 Cycle 1 or 2
	N=132*	N=130*
Thrombocytopenia	50 (37.9%)	57 (43.8%)
Neutropenia	42 (31.8%)	46 (35.4%)
Anemia	42 (31.8%)	48 (36.9%)
Fatigue	22 (16.7%)	31 (23.8%)
Constipation	25 (18.9%)	21 (16.2%)
Nausea	21 (15.9%)	23 (17.7%)
Leukopenia	22 (16.7%)	25 (19.2%)
Diarrhea	14 (10.6%)	19 (14.6%)
Febrile neutropenia	10 (7.6%)	18 (13.8%)
Headache	18 (13.6%)	19 (14.6%)

The INQOVI label has updated Adverse Reactions ( $\geq 10\%$ ) in Patients Who Received INQOVI in Pooled Safety Population.

In this trial, participants with higher risk MDS (defined as intermediate risk, high risk & very high risk, will be enrolled. IPSS-R score at baseline is a crucial clinical indicator in the sense it will inform about the treatment outcomes and prognostic of each given Participant. Each level of risk (intermediate/high/very high) is associated with a different survival length and potential of leukemic transformation. From previously reported real world evidence studies, despite the availability of HMA therapies, the risk of death and AML transformation was high. Higher-risk MDS patients had the poorest prognosis, with a median overall survival time less than 1 year from HMA initiation and a median time to AML transformation of less than 2 years from HMA initiation ([Stein et al 2019](#)).

[figure not shown]
Novel targeted therapies and immune checkpoint inhibitors are being clinically studied in MDS. Blocking Programmed cell death protein 1/ligand (PD-1/PD-L1) or Cytotoxic T Lymphocyte Associated Protein 4 (CTLA4) pathways enhances anti-leukemia responses by unleashing Tcells in murine models of AML/MDS. In addition, there is evidence of pharmacodynamic activity and promise for checkpoint inhibition in MDS ([Chen et al 2008](#), [Zhang et al 2009](#), [Yang et al 2014](#), [Kong et al 2015](#), [Ørskov et al 2015](#)); however, it will be important to determine the ideal checkpoint inhibitor strategy and to consider combination therapies in order to optimize anti-tumor immunity. A few clinical trials have investigated immune checkpoint inhibitors in MDS and AML patients. An ongoing Phase II study investigates the clinical effects of the checkpoint inhibitors nivolumab (PD1) and ipilimumab (CTLA4) with or without the hypomethylating agent azacitidine in front-line and relapsed MDS patients. Front-line MDS patients were treated with the combination azacitidine+nivolumab or ipilimumab, whereas relapsed MDS patients received single-agent nivolumab or ipilimumab. Twenty patients were treated with azacitidine+nivolumab, 21 with azacitidine+ipilimumab, 15 with nivolumab, and 20 with ipilimumab. The observed overall response rate was 75% (15/20), 71% (15/21), 13% (2/15), and 35% (7/20) of patients treated with azacitidine combined with nivolumab,

azacitidine combined with ipilimumab, nivolumab, and ipilimumab, respectively; Complete Remission or Complete Remission with residual thrombocytopenia was observed in 10/20 (50%), 8/21 (38%), 0 (0%), and 3 (15%) in patients treated with azacitidine combined with nivolumab, azacitidine combined with ipilimumab, nivolumab, and ipilimumab, respectively.

[figure not shown]
Main toxicities reported were as follows: skin rash (11%); fatigue (9%); pain (7%); infection (6%); febrile neutropenia (5%); pruritus (6%); diarrhea (5%); constipation, nausea (4% each), alanine aminotransferase (ALT) elevations, anorexia, cough (3% each). This provides preliminary evidence that checkpoint inhibition combined with hypomethylating agents is feasible in front-line MDS and may have clinical activity ([Garcia-Manero et al 2018](#)). A Phase Ib/II study involving azacitidine and nivolumab has been conducted in 70 relapsed/refractory AML patients. The overall response rate (ORR) in this study was 33%: 23 clinical responses were reported including 4 complete remission, 11 complete remission with insufficient recovery of counts (CRi), 1 partial remission (PR), and 7 patients with hematologic improvement (HI) maintained > 6 months. The ORR was 58% and 22% in HMA-naive (n = 25) and HMA pretreated (n = 45) patients, respectively. Duration of response among responders was 5.2 months. Three patients in CR/CRi underwent HSCT. Additionally, 6 patients had stable disease lasting for more than 6 months.

Overall the combination azacitidine plus nivolumab was well tolerated, Grade 3 or 4 immune related adverse events (irAE) occurred in 8 (11%) patients ([Daver et al 2019](#)). A Phase Ib study reported that ipilimumab in patients with MDS after HMA failure is safe but has limited efficacy as monotherapy. However, prolonged stable disease was reported and some patients received allo HSCT. Prolonged stable disease for  $\geq$  46 weeks occurred in 7 patients (24% of the patients), including 3 patients with more than a year of stable disease. Five patients underwent allografting without excessive toxicity ([Zeidan et al 2018](#)).

T-cell immunoglobulin and mucin domain-containing 3 (TIM-3) is an inhibitory cell surface receptor with a key role in regulating adaptive and innate immune responses). TIM-3+ hematopoietic stem cells from patients with MDS display aberrant differentiation, increased proliferation and decreased apoptosis ([Sakuishi et al 2011](#)). TIM-3 is also preferentially expressed on leukemic stem cells and blasts, and expression of TIM-3 correlates with severity of MDS. Therefore the blockade of TIM-3 constitutes a potential target for novel therapies in MDS, and promising preclinical and clinical anti-cancer activity has been reported for TIM-3 blockade ([Kikushige et al 2010](#), [Sakuishi et al 2010](#), [Ngiow et al 2011](#), [Sakuishi et al 2011](#), [Jing et al 2015](#), [Asayama et al 2017](#)).

